## 13.7 Reporting and Exclusions

### 13.7.1 Evaluation of Toxicity

All participants will be evaluable for toxicity from the time of the first dose of enoxaparin.

### 13.7.2 Evaluation of the Primary Efficacy Endpoint

All participants will be assessed for primary endpoints as long as received at least 1 dose of enoxaparin following randomization.

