**5.2.3 Day 14 -4, + 7 days**

Enoxaparin should be continued until either hospital discharge or day 14. After receiving the final dose of enoxaparin no additional doses of enoxaparin on study will be administered. Assessment for evidence of major hemorrhage or VTE will be recorded. After the day 14 clinical assessment, study staff will become unblinded to treatment allocation in order to appropriately schedule a bilateral lower extremity ultrasound for study subjects on Arm A (see 5.3 below). For participants who remain hospitalized, study subjects should continue with standard pharmacologic thromboprophylaxis per the discretion of the treating physician. Day 14 symptom assessment can be performed by phone.

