**5.3 Off treatment procedures (unblinding)**

Following the completion of the day 14 assessment, study staff will contact a clinical research pharmacist at BIDMC. Criteria for off treatment will be reviewed and then the study staff will be informed as to whether the participant was previously assigned to Arm A (standard enoxaparin) versus Arm B (weight-based enoxaparin). For participants randomized to Arm A, a bilateral ultrasound will be scheduled (see study calendar) to evaluate for asymptomatic deep vein thrombosis.

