9.2.1.3 Site Performing Correlative Studies: BIDMC

## 10. STUDY CALENDAR

Baseline evaluations are to be conducted within 48 hours prior to start of protocol therapy.

Event/Procedure	Screening/ Pre-treatment	Day 1	Days 2-6 a	Day 7 a,c	Days 8-13 a	Day 14	Day 17
Day Range	-2 to 0			± 1 day		-4, +7 days	± 5 days
Eligibility Assessments	X						
Informed Consent	X						
Inclusion/Exclusion Criteria	X						
Medical History	X						
ECOG Performance Status Score	X						
Concomitant medication review	X			X		X	
Randomization	X						
Administer enoxaparin		X	X	X	X	X	
Clinical Assessments							
Physical examination including vital signs, and height	X						
Clinical Prediction Score data collection	X						
Weight	X			X			
Assessment of signs and symptoms of VTE and bleeding	X			X		X	
Laboratory Tests							
Plasma storage for correlative studies	X						
Complete blood count	X d	X		X			
PT/PTT	X						
Creatinine	X	X		X			
AST/ALT	X						
Imaging							
Bilateral lower extremity ultrasound							X b

a: Study subjects will only remain on treatment while hospitalized or until day 14, whichever comes first.

b: Arm A ONLY (standard dose enoxaparin).

c: Day 7 study visit not mandatory if participant is no longer hospitalized.

d: Also record CBC from initial admission

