## 11. MEASUREMENT OF EFFECT

### Venous Thromboembolism (VTE)

Cumulative incidence of venous thromboembolic events is the primary endpoint for Arm A and a secondary endpoint for Arm B. ***The composite endpoint includes objectively confirmed proximal or distal lower extremity DVT, subsegmental or larger pulmonary embolism; or fatal PE diagnosed by autopsy.*** All other venous or arterial events will be recorded and analyzed as secondary endpoints (including central line associated DVT).

Participants presenting with symptoms compatible with DVT and/or PE will undergo radiographic imaging with compression ultrasound, VQ lung scan, or spiral CT. Confirmed episodes of VTE will be managed by the treating physician per standard of practice.

Presence of any of the following will be considered diagnostic for a VTE:

- New non-compressibility of lower extremity deep venous segments by compression ultrasound.
- Intraluminal defects in two or more views on pulmonary angiography
- Sudden contrast cut-off of one or more vessels greater than 2.5 mm in diameter on a pulmonary angiogram
- A high probability VQ lung scan showing one or more segmental perfusion defects with corresponding normal ventilation (mismatch defect)
- Abnormal spiral CT showing thrombus in pulmonary vessels (subsegmental or larger)

Those VTE that do not qualify for the primary endpoint such as a central line-associated thrombus will be recorded and analyzed as secondary endpoints.

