#### **13.2 Sample Size, Accrual Rate and Study Duration**

The documented incidence of VTE in cancer patients in randomized clinical trials ranges considerably (3-17%) on pharmacologic thromboprophylaxis at standard prophylactic dosing.[8] With the additional incorporation of tumor-specific thrombotic risk assessment, we anticipate the incidence of VTE for high risk cancer patients receiving fixed standard dose enoxaparin will be greater than 10%, especially with inclusion of protocol-mandated lower extremity ultrasounds.

We plan to enroll a total of 50 high risk cancer patients between Beth Israel Deaconess Medical Center and Cleveland Clinic Foundation, of which 25 will be randomized to standard dose enoxaparin. Assuming a cumulative incidence of thrombosis at day 17 is 12% (90% binomial confidence interval 3.3 to 28.2%), While we anticipate an increased risk of major hemorrhage observed in cancer patients compared to that of general medical patients, we expect these events to be rare. Point estimates of hemorrhage endpoints at Day 14 will be provided along with the 90% exact binomial confidence intervals. The point estimate will serve to inform sample size calculations for a larger phase III clinical trial.

The trial will only be open at BIDMC and Cleveland Clinic and we anticipate enrolling 3 patients per month.

Participants who receive at least one dose of treatment post-randomization will be considered evaluable for the study.

Accrual Targets				
Ethnic Category	Sex/Gender			
	Females		Males	
Hispanic or Latino	13	+	12	= 25
Not Hispanic or Latino	12	+	13	= 25
Ethnic Category: Total of all subjects	25 (A1)	+	25 (B1)	= 50 (C1)
Racial Category				
American Indian or Alaskan Native		+		=
Asian	3	+	2	= 5
Black or African American	5	+	6	= 11
Native Hawaiian or other Pacific Islander		+		=
White	17	+	17	= 34
Racial Category: Total of all subjects	25 (A2)	+	25 (B2)	= 50 (C2)
	(A1 = A2)		(B1 = B2)	
			(C1 = C2)	

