### 13.5 Analysis of Primary Endpoints

Cumulative incidence of VTE at day 17 (in arm A) and major hemorrhage endpoints at day 14 (both arms) will be calculated along with their 90% exact binomial confidence intervals.

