## 13.6 Analysis of Exploratory Objectives

13.6.1 Efficacy analysis: Although the study is not formally powered to determine efficacy, we will perform a secondary analysis to preliminarily compare the cumulative incidence of symptomatic VTE (data collected prior to unblinding) for the standard dose(Arm A) versus intermediate dose enoxaparin (Arm B). Accordingly, assuming a VTE event rate of 25% which is towards the upper end of the binomial confidence interval in the standard enoxaparin arm compared with a 0% event rate in the intermediate dose enoxaparin arm, the power of the study is 0.74 with a one-sided  $\alpha$  of 0.05. The cumulative incidence rate of VTE at day 17 will be estimated using the competing risk method, where VTE is the primary event and death is considered the competing event.[31]

13.6.2 Prediction models: For each of the three scoring systems (Padua, Khorana, IMPROVE), we plan to assess the 2 by 2 contingency table distributions while changing the score cut-offs (such as a Padua score  $\geq 6$  or an IMPROVE scores  $\geq 5$  or a Khorana score  $\geq 3$ ) in order to evaluate whether the classification probabilities (particularly specificity and sensitivity) change based on the chosen cut-off. The goal is to see if we can determine a more stringent cut-off (compared to a Padua score  $\geq 4$ ) by considering the Padua scoring system and/or the other 2 scoring systems to further refine hospitalized cancer patients at high risk of VTE. We aim at maintaining 100% sensitivity, while improving the specificity of the refined risk model. We fully recognize that based on the limited number of patients enrolled that we will have limited power to determine definitively whether the additional risk models can reliably improve specificity without impacting sensitivity. Therefore, we do not plan on utilizing these data to refine the inclusion/exclusion criteria for the planned phase III trial, but rather will confirm the findings within the phase III trial through stratification at time of randomization.

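### Read literally, the one-dose rule with an exact binomial counts a dosed Arm A patient who has no day-17 scan and no confirmed VTE as a non-event, so missed scans would bias the primary VTE rate low

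*Combined protocol and SAP*

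**What the plan says.** **Who is counted.** Section 13.7.2: "All participants will be assessed for primary endpoints as long as received at least 1 dose of enoxaparin following randomization". Sections 5.1 (under Arm B) and 13.2 carry the same rule: "Participants who receive at least one dose of treatment post-randomization will be considered evaluable for the study". No section makes the ultrasound a condition of being evaluable.

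**How the rate is estimated.** Under section 13.5, Arm A VTE at day 17 and major hemorrhage at day 14 "will be calculated along with their 90% exact binomial confidence intervals". Section 13.2 illustrates this for 25 Arm A patients with a 12% incidence and an interval of 3.3 to 28.2%. It adds that the point estimate will inform phase III sample size.

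**What is an event.** Section 11: "The composite endpoint includes objectively confirmed proximal or distal lower extremity DVT", confirmed pulmonary embolism, or fatal pulmonary embolism at autopsy.

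**How silent DVT is found.** Section 5.3 provides that, for Arm A, "a bilateral ultrasound will be scheduled (see study calendar) to evaluate for asymptomatic deep vein thrombosis". The study calendar places this scan at day 17 ± 5 days, in Arm A only. The preceding visit is different in kind: "Day 14 symptom assessment can be performed by phone" (section 5.2.3).

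**The other estimator.** Section 13.6.1, under exploratory objectives, says "The cumulative incidence rate of VTE at day 17 will be estimated using the competing risk method", with death as the competing event. It gives no censoring rule.

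**The concern.** A patient can be dosed, be discharged, complete day 14 by telephone and never attend for the scan. Such a patient is evaluable under the one-dose rule. With no scan, a silent DVT cannot be confirmed, so unless a symptomatic VTE is confirmed the patient can only fall in the non-event cell of a binomial. An unscanned patient with a confirmed symptomatic VTE is still an event and is not part of the problem.

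Missed scans are foreseeable. Treatment ends at discharge, patients with ECOG status 3 or 4 are eligible, and section 5.8 anticipates loss to follow-up and death. Section 13.2 itself relies on the scans for its expectation of a rate above 10%.

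Estimation is the purpose of this trial. A rate that falls as fewer patients are scanned, with an interval that narrows at the same time, would carry into phase III planning with more apparent precision than the data hold.

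**Working it through.** **1. The plan's own figure.** The exact (Clopper–Pearson) 90% interval for 3/25 is 3.35% to 28.17%, matching the 3.3 to 28.2% in section 13.2 to within rounding. The illustration is therefore three events over all 25 Arm A patients. Its width is 28.17 − 3.35 = 24.8 points.

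**2. Inputs.** From the documents: n = 25 and true rate p = 12%. Not in the documents, so assumed: m, the share of dosed Arm A patients unscanned (10–40%), and s, the share of VTE found only by scan (25–100%).

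**3. Expected rate, scans missed independently of VTE.** A VTE is lost only if it is scan-only and the patient is unscanned, so the expected rate is p(1 − s·m) and the shortfall is p·s·m.

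| m | s | expected rate | shortfall (points) |
|---|---|---|---|
| 0% | any | 12.0% | 0 |
| 10% | 25% | 0.12 × (1 − 0.025) = 11.7% | 0.3 |
| 20% | 75% | 0.12 × (1 − 0.15) = 10.2% | 1.8 |
| 30% | 75% | 0.12 × (1 − 0.225) = 9.3% | 2.7 |
| 40% | 100% | 0.12 × (1 − 0.40) = 7.2% | 4.8 |

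**4. Scans missed in relation to VTE.** Let unscanned patients have R times the VTE risk of scanned patients, with 12% overall. Scanned risk is 0.12/(1 − m + mR), and the shortfall is m·s·R times that. At m = 20%, s = 75%:
- R = 2: scanned risk 0.12/1.2 = 10%; shortfall 0.20 × 0.75 × 20% = 3.0 points.
- R = 0.5: scanned risk 0.12/0.9 = 13.3%; shortfall 0.20 × 0.75 × 6.7% = 1.0 point.

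The size moves around 1.8 points; the direction does not change.

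**5. Effect on the interval.** This is by exact enumeration, n = 25, no deaths. X1 ~ Bin(25, p(1−s)) is VTE confirmed without a scan, U ~ Bin(25−X1, m) is unscanned, and X2 ~ Bin(25−X1−U, ps/(1−p(1−s))) is scan-detected. For all dosed patients:

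| | all scanned | m = 30%, s = 75% | m = 40%, s = 100% |
|---|---|---|---|
| mean estimate | 12.0% | 9.3% | 7.2% |
| mean 90% width (points) | 23.9 | 21.8 | 20.0 |
| coverage | 93.5% | 90.7% | 84.4% |
| wholly below 12% | 4.1% | 8.7% | 15.4% |

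**6. Competing-risk alternative.** With unscanned event-free patients censored at day 14, the estimate is a + (1 − a − d)h. Here a is symptomatic VTE/25, d is deaths without VTE/25, and h is scan-positive/scanned. At m = 30%, s = 75% it averages 12.0%, with a root mean square error (RMSE) of 7.6 points against 6.4 for the all-dosed rate.

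**7. A tempting repair that fails.** Restricting the denominator to patients scanned or with confirmed VTE gives p(1 − sm)/[1 − m + m·p(1 − s)]. At m = 30%, s = 75% this is 0.093/(0.70 + 0.30 × 0.03) = 0.093/0.709 = 13.1%, which errs high.

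**8. One data set, three answers.** Take 25 dosed: 1 symptomatic VTE, 18 scanned with 2 DVT, 6 unscanned and event-free, no deaths.
- Unscanned as non-events: 3/25 = 12.0% (90% interval 3.35–28.17%).
- Competing-risk: 1/25 + (24/25)(2/18) = 14.7%.
- Unscanned as events: 9/25 = 36.0% (20.2–54.4%).

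**The case against.** **The coding is inferred.** Section 13.7.2 says who is assessed, not how a missing assessment is scored. Section 13.2 treats the scans as required by protocol. A reader might infer that the plan declares unscanned patients VTE-free; it does not. This stands, and it is why the point is put as a literal reading. Even so, the stated denominator, event definition and binomial together leave no other cell for such a patient, so this is more than a missing detail.

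**Sections 13.5 and 13.6.1 need not conflict.** A reader might infer two contradictory primary estimators. With nobody censored, the competing-risk incidence equals x/25, so they diverge only when scans are missing. This also stands. But section 13.6.1 sits under the exploratory heading and has no censoring rule, so it does not settle the missing-scan case.

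**The size is assumed and mostly small.** The large figures need both 40% unscanned and every VTE scan-only. Across the 16 combinations of 10, 20, 30, 40% unscanned and 25, 50, 75, 100% scan-only, the all-dosed interval keeps at least 90% coverage in 13. A reader might infer that the primary result will be badly wrong; the documents do not support that.

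**The unbiased estimator costs precision.** Its RMSE was larger in all 16 combinations. Preferring it at n = 25, under an untestable missing-at-random assumption, is a judgement. This stands, so the fix does not impose it.

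**Conclusion.** The concern holds in a limited form and should be addressed. Applied as written, the rules score a dosed, unscanned, event-free Arm A patient as a non-event. Any missed scan then pushes the primary VTE estimate down whenever some VTE is detectable only by scan.

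For a true 12%, the expected shortfall is 0.3 to 4.8 points over the assumed ranges, and 2.7 points at 30% unscanned and 75% scan-only. These sizes rest on two shares the documents do not give and on scans being missed independently of VTE. If that independence fails, the size changes but not the direction. With full scanning there is no bias. The shift is modest beside a planned interval of about 25 points, but it is systematic and falls on a quantity meant for phase III planning.

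It does not follow that the binomial analysis is invalid, or that one particular replacement is required.

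**What to change.** In sections 13.5 and 13.7.2:

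1. State that a dosed Arm A patient with no scan and no confirmed VTE is not counted as known to be VTE-free at day 17.
2. Report the number of Arm A patients scanned. Give x/25 with its exact 90% interval (unscanned as non-events) as the lower bound, and the rate with unscanned patients as events as the upper bound.
3. Say whether the competing-risk method of section 13.6.1, with death competing, governs the primary day-17 estimate. If so, state that unscanned event-free patients are censored at their day 14 assessment. The day 14 window runs to +7 days, so a late call must not carry such a patient to day 17 as a non-event.

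Do not simply restrict the denominator to patients scanned or with confirmed VTE.

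Assigning visits to nominal days would also deal with scans on days 18–22, and an exact interval at the effective sample size could accompany the competing-risk estimate. Both are optional. That interval is conservative (about 97% coverage for a nominal 90%, mean width 27.8 points, at 30% and 75%). A nominal-day rule must also place symptomatic VTE after an early negative scan, and deaths on days 15–17.

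**Cost.** Wording and one table; no extra scans. If the competing-risk estimate is adopted, expect a wider interval and larger RMSE (7.6 against 6.4 points at 30% and 75%) under missing at random, which is why both bounds belong in the report.

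**Separately.** Section 5.6 opens by coupling stopping enoxaparin with leaving the study but closes with removal from protocol therapy only, while sections 5.7 and 5.8 imply continued follow-up. Reconcile these on whether patients taken off enoxaparin keep the day 14 and day 17 assessments.

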## 14. PUBLICATION PLAN

The results should be made public within 24 months of reaching the end of the study. The end of the study is the time point at which the last data items are to be reported, or after the outcome data are sufficiently mature for analysis, as defined in the section on Sample Size, Accrual Rate and Study Duration. If a report is planned to be published in a peer-reviewed journal, then that initial release may be an abstract that meets the requirements of the International Committee of Medical Journal Editors. A full report of the outcomes should be made public no later than three (3) years after the end of the study.

**15. APPENDIX A      PERFORMANCE STATUS CRITERIA**

ECOG Performance Status Scale		Karnofsky Performance Scale	
Grade	Descriptions	Percent	Description
0	Normal activity. Fully active, able to carry on all pre-disease performance without restriction.	100	Normal, no complaints, no evidence of disease.
		90	Able to carry on normal activity; minor signs or symptoms of disease.
1	Symptoms, but ambulatory. Restricted in physically strenuous activity, but ambulatory and able to carry out work of a light or sedentary nature (e.g., light housework, office work).	80	Normal activity with effort; some signs or symptoms of disease.
		70	Cares for self, unable to carry on normal activity or to do active work.
2	In bed <50% of the time. Ambulatory and capable of all self-care, but unable to carry out any work activities. Up and about more than 50% of waking hours.	60	Requires occasional assistance, but is able to care for most of his/her needs.
		50	Requires considerable assistance and frequent medical care.
3	In bed >50% of the time. Capable of only limited self-care, confined to bed or chair more than 50% of waking hours.	40	Disabled, requires special care and assistance.
		30	Severely disabled, hospitalization indicated. Death not imminent.
4	100% bedridden. Completely disabled. Cannot carry on any self-care. Totally confined to bed or chair.	20	Very sick, hospitalization indicated. Death not imminent.
		10	Moribund, fatal processes progressing rapidly.
5	Dead.	0	Dead.

## 16. APPENDIX B: SPECIMEN COLLECTION INSTRUCTION AND SHIPPING REPORT

### Instructions for Samples collection:

1. **Approximately 10ml of blood** will be drawn into blue top tubes (3.2% citrate) in either two 5ml tubes or one 15ml tube.
2. **First spinning (centrifugation)** should be done within 1 hour of specimen collection. Spin samples at 2100 x G for 20 minutes.
3. Transfer plasma using transfer pipettes to 20cc tube (leave red cell layer undisturbed to be discarded).
4. The plasma supernatant will be transferred to a clean single tube leaving the 1ml at the bottom of the tube undisturbed (to be discarded) and then the plasma layer has to be centrifuged a second time at 2100 x G x 20 minutes.
5. The transferred plasma will be aliquoted into 4-6 cryotubes (up to 500 $\mu$ l per tube) labeled screening visit. Leave the plasma at the bottom of the tube undisturbed (to be discarded).
6. **Label all cryotubes** with the provided pre-filled labels
7. Place tube in biohazard bag and inside an insulated shipper (cooler) with the appropriate quantity of dry ice. Ship sample along with the shipment report form.

Tubes can be stored locally at -80°C and/or batch sent on dry ice to:

Address:

8. Please email study staff at [XXX](#) to inform her that samples have been sent.

### Specimen Shipment Report

**Medical Center:** \_\_\_\_\_

**Study ID#:** \_\_\_\_\_

**Collection Date:** \_\_\_\_ / \_\_\_\_ / \_\_\_\_

**Time of draw:**   :   AM/PM

**Number Samples sent:** \_\_\_\_\_

**Time of spin:**   :   AM/PM

**Number Samples store:** \_\_\_\_\_

**Completed By:** \_\_\_\_\_

**Comments:**

**Contact Study Coordinator at Medical Center:** \_\_\_\_\_

**Phone:** \_\_\_\_\_ **Email:** \_\_\_\_\_

**This complete form and samples should be mailed to the below address.  
Please call or email study staff at BIDMC the day the shipment is sent out.  
Thank you!**
